Objectives and endpoints

The primary objective is to assess the safety and tolerability of a peptide vaccine containing the enzyme arginase-1 (ARG1) with Montanide ISA 51 as adjuvant in patients with metastatic and treatment-refractory solid tumors. The primary endpoint is adverse events (AE) assessed by Common Terminology Criteria for Adverse Events (CTCAE) 4.0 and laboratory monitoring.

The secondary objective is to evaluate the immune response before, during and after treatment. The endpoint is responses of ARG1 specific T cells measured by ELISPOT and cytokine release assays.

The exploratory objective is to evaluate the clinical efficacy of the treatment. The endpoints are objective response (OR), progression free survival (PFS) and overall survival (OS).

Protocol synopsis

Background

Metastatic solid tumors are regarded incurable and fatal despite great progresses in medical oncology over the past decade. Treatment options are in end-effect palliative and given with the purpose of prolonging life. Standard therapies for metastatic solid tumors range from hormone suppression to aggressive chemotherapy regimens, but in the last couple of years immunotherapy has revolutionized several cancer treatments. This protocol describes a new approach in the treatment of patients with metastatic solid cancer by modulating the tumor microenvironment using a peptide vaccine.

The unregulated growth of cancer cells is only possible when the immune system does not launch an effective antineoplastic response. Cancer cells highjack the system of checks and balances in the immune system by exploiting the system of local adaptive immune resistance. One mechanism utilized by malignant cells is the overexpression of the immunosuppressive enzyme arginase-1 (ARG1).

ARG1 is an enzyme expressed by some cancer cell lines and different myeloid cells in the immunosuppressive tumor microenvironment. ARG1 catalyzes the conversion of the amino acid arginine to ornithine and urea. A depletion of arginine suppresses T cell function through the impairment of the T cell receptor (TCR)-complex resulting in immunosuppression in a cancer setting.

The theoretic background for a peptide vaccine against ARG1 is to boost the activity of ARG1-specific T cells to eliminate immune cells that express ARG1 as part of the local immunosuppressive microenvironment in cancerous tissues.

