Monitoring of the trial will be done by the GCP unit at the University of Copenhagen. It is expected that the responsible GCP unit will contact and visit the principal investigator on a regular basis and request for access to monitoring of the different source documents in relation to the trial (Case Report Forms and other relevant documents).

Audit from the Danish Medicines Agency and other health authorities are likewise allowed on request. Monitor has access to laboratory test results and other participant information needed to verify the entries made in the Case Report Forms. The principal investigator (or his/her substitute) agrees to cooperate with the monitor so that potential problems discovered during the monitoring process will be solved.

Statistical considerations

The study is a phase I trial with the primary objective to evaluate safety of the combination therapy. Since the trial is a first in human study, a formal sample size calculation cannot be performed. From experience with similar studies, it is deemed appropriate to include 10 participants.

Ten participants are deemed sufficient to evaluate safety and considered safe if less than 20 % experience grade 3-4 AE.

All participants that are included and treated according to the protocol will be included in the statistical analyses. Participants who are excluded before receiving treatment will not be included in the statistical analyses:

- Where the inclusion criteria at baseline are not fulfilled
- Patients withdraw their consent
- Have started other treatment

For immunological responses, the 95 % confidential interval will be calculated for patient data and for response rates descriptive statistics will be used.

Effect parameters

Primary effect parameter

Primarily, safety and tolerability of the combination therapy is assessed. This is done by registration of all adverse events and possible unwanted events that occur in relation to the

treatment and in accordance with the CTCAE criteria. Data collection will take place in accordance with the data source list.

Secondary effect parameter

For the assessment of the immunological response, ARG1-specific T cells responses will be identified by the use of ELISPOT technology and antigen specific populations will be characterized for their cytokine secretion pattern.

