Patients included in the trial will have additional blood tests performed compared to patients receiving standard treatment. The amount of blood and the specific procedure when taking a blood sample are not associated with any significant risk. There is a minimal risk of bleeding and infection and pain and bruising can occur in the area.

Tumor biopsies will be taken by experienced doctors, and is not associated with any significant risk; again there is a small risk of bleeding and infection and pain and bruising might also occur in the area.

CT scans and PET-CT scans are not considered a risk based on the low dose radiation. Both full body CT and PET-CT scans give a radiation doses of around 15 milliSievert (mSv), which is about 5 times the annual background radiation^{61,62}. The contrast used can very rarely cause allergic reactions and brief reduction in renal function; therefore patients are screened by standard procedures prior to the examination.

Monitoring of toxicity

Adverse events

Adverse events (AE) are defined as any undesirable experience occurring to a subject during a clinical trial, whether or not considered related to the investigational treatment. All AEs reported spontaneously by the subject or observed by the investigator or his staff will be recorded and described in the patient chart and the electronic Case Report Form (eCRF). The severity and consequences will be recorded for each AE. The severity and relation to the study medication will be assessed in accordance with the guidelines described in the following.

The investigator must attempt to identify all clinical and objective events from patients receiving treatment and determine their relation to the study medication. The investigator determines the relationship between AEs and treatment using the following guidelines:

Grading of adverse events

The severity of an AE refers to the intensity of the reaction.

Events are graded using CTCAE version 4.0. The following scale can be used if this grading is not applicable:

- 1 = light
- 2 = moderate
- 3 = severe
- 4 = life threatening
- 5 = lethal

Patients experiencing AEs will be monitored with the relevant clinical evaluations and laboratory investigations assessed by the attending physician. All AEs must be monitored until satisfactory restitution or stabilization. Results of the monitoring must be recorded in the patient chart and eCRF.

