Abnormal laboratory tests are not to be recorded in the eCRF unless they have caused a clinical event, resulted in termination of the treatment or otherwise meet the criteria of a serious AE (see the following).

Serious adverse events

A serious adverse event (SAE) is to be reported to sponsor within 24 hours and is defined as any medical occurrence or effect that occurs at any dose:

- results in death;
- is life threatening (at the time of the event);
- requires hospitalization or prolongation of existing patients' hospitalization;
- results in persistent or significant disability or incapacity;
- leads to a congenital anomaly or birth defect;
- is a significant medical event

Adverse reactions

An adverse reaction (AR) can be expected if described in the IMPD or the relevant product summary, or unexpected if the grade or severity does not correlate with the product information in the before mentioned documents.

If the AR is unexpected, meets the criteria of a serious adverse reaction (SAR) and is found related to the investigational treatment, it is classified as a suspected unexpected serious adverse reaction (SUSAR). As this is a First in human trial, the SARs are difficult to classify as "expected" or "unexpected." Therefore, SARs will be reported as SUSARs.

Reporting of adverse events and adverse reactions

Investigator reports SAEs, SARs and SUSARs to sponsor within 24 hours. Sponsor reports SARs and SUSARs to the Danish Medicine Agency within 7 days if considered life threatening or fatal, and otherwise within 15 days. Consequences for the study must be reported. Sponsor submits a list annually that summarizes any SARs and SUSARs as well as a report regarding the study patients' safety to the Danish Medicine Agency and the Research Ethics Committee (investigator can report to the Research Ethics Committee as well).

Sponsor submits a final report to the Danish Medicine Agency at the end of the study, with a description of all SAEs, SARs and SUSARs.

The following is not to be reported:

- Deaths caused by the malignant disease or progression
- Hospitalizations or prolongation of current hospitalization caused by the malignant disease:
 - weight loss
 - fatigue
 - electrolyte derangement
 - pain management
 - anxiety
 - palliative hospitalization
 - stay at hospice or terminal care
 - progression of the underlying disease
- Hospitalizations or prolongation of current hospitalization if the sole reason for hospitalization or prolongation is:

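### The eCRF rule for abnormal laboratory tests can leave transient, isolated grade 3 laboratory toxicity out of the safety record, although laboratory monitoring is part of the primary endpoint

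*Combined protocol and SAP*

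**What the plan says.** Under *Objectives and endpoints*: "The primary endpoint is adverse events (AE) assessed by Common Terminology Criteria for Adverse Events (CTCAE) 4.0 and laboratory monitoring". Under *Primary effect parameter*, safety is assessed by "registration of all adverse events and possible unwanted events" according to CTCAE, and "Data collection will take place in accordance with the data source list". That list is not among the documents.

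Under *Monitoring of toxicity – Adverse events*, AEs reported by the patient or "observed by the investigator or his staff will be recorded and described in the patient chart and the electronic Case Report Form (eCRF"). Under *Grading of adverse events*: "Patients experiencing AEs will be monitored with the relevant clinical evaluations and laboratory investigations assessed by the attending physician", and then "Results of the monitoring must be recorded in the patient chart and eCRF". The very next sentence is the restriction: "Abnormal laboratory tests are not to be recorded in the eCRF unless they have caused a clinical event, resulted in termination of the treatment", with a third exception for abnormalities that meet the criteria of a serious AE.

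Two decisions count grade 3-4 AEs. *Statistical considerations* takes 10 participants as enough, with the treatment "considered safe if less than 20 % experience grade 3-4 AE". *Study design* stops the trial if 3 or more patients have drug-related grade 3-4 AEs. Neither wording sets laboratory events apart.

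**The concern.** The restriction is a stated rule, not a missing detail. Followed as written, it keeps some CTCAE-graded laboratory toxicity out of the case report form of a first-in-human safety trial.

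The laboratory component is not incidental here. The protocol says ARG1 is expressed mainly in hepatocytes (*The ARG enzyme*) and names interference with the urea cycle in the liver as a potential concern (*Peptide vaccine safety*). Liver enzymes are among the values that can fall into the gap.

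At stake are the completeness of the AE dataset and the proportion compared with 20%. In a trial of 10, that proportion is decided by one patient.

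**Working it through.** **Step 1. Is a graded laboratory value an AE in this protocol?** The AE definition does not say so outright. Two places support it. The delay and exclusion tables under *Criteria for treatment modifications* and *Criteria for end of treatment* give grades to blood values and continue with rows for other AEs. *Risk evaluation – Autoimmunity* lists anemia and increased ALT among the treatment-related AEs of the oral arginase inhibitor, and suggests that its AEs may indicate what to expect in this trial.

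**Step 2. Which passages are inconsistent with the restriction?**

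- *Objectives and endpoints*: laboratory monitoring belongs to the primary endpoint, but the restriction keeps most of its abnormal findings out of the eCRF. The endpoint text does not itself mention the eCRF.
- *Primary effect parameter* and *Adverse events*: all AEs are to be registered. This conflicts with the restriction on the reading in step 1.
- The closing sentence on monitoring results: it concerns patients who already have an AE, so it conflicts only for laboratory results obtained during that follow-up.

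**Step 3. Which grade 3 values escape every exception?** The delay limit is compared with the exclusion limit. A value beyond the first but short of the second postpones a vaccination without ending treatment.

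| Test | Postpones at | Excludes at | Band between |
|---|---|---|---|
| Leukocytes (x 10^9) | < 1.5 | < 1.0 | 1.0 to < 1.5 |
| Neutrophils (x 10^9) | < 1.0 | < 0.5 | 0.5 to < 1.0 |
| Thrombocytes (x 10^9) | < 50 | < 25 | 25 to < 50 |
| Hemoglobin (mmol/l) | < 5 | < 4 | 4 to < 5 |
| Creatinine (x upper limit) | > 3 | > 4.5 | > 3 to 4.5 |
| ASAT (x ULN) | > 5 | > 8 | > 5 to 8, without the bilirubin rise in the footnotes |
| ALAT (x ULN) | > 5 | > 8 | > 5 to 8, without the bilirubin rise in the footnotes |
| Bilirubin (x ULN) | > 3 | no stand-alone value visible | unclear |

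Seven of eight tests have such a band. A value in it that causes no symptoms and resolves without ending treatment meets no exception, unless the investigator judges it a significant medical event and hence serious. For bilirubin, a row or footnote mark may have been lost in reading the table, so nothing is concluded.

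Still recorded are the listed grade 4 values, the transaminase-bilirubin combinations in the footnotes, grade 3 events under the catch-all exclusion row, the hospitalisations that the reporting section sends to the eCRF, and anything serious.

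**Step 4. What can an omission do to the 20% criterion?** The proportion is patients with a grade 3-4 AE divided by patients analysed. An uncounted patient lowers the numerator and leaves the denominator unchanged, so the proportion can only fall.

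- n = 10: 2/10 = 20.0% (not below 20%); 1/10 = 10.0% (below).
- Patients excluded before the second vaccine are replaced, so 11 or 12 could be treated. n = 11: 3/11 = 27.3% against 2/11 = 18.2%. n = 12: 3/12 = 25.0% against 2/12 = 16.7%.

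In each case the boundary is one patient wide.

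**Step 5. And to the stopping rule?** If the running tally came from the eCRF, one uncounted patient would turn 3 (stop) into 2 (continue). This is less likely than the effect on the final proportion. AEs are recorded at attendance (*Assessment of safety*), go/no-go evaluations separate the first patients (*Initial patient enrollment and treatment*), and CRF registration follows the course of treatment (*Data registration*).

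**The case against.** The best defence is that the restriction is a specific rule for when a bare laboratory value becomes reportable, sitting under a general rule for AEs. The tests are scheduled at every vaccination visit, the values remain in chart and laboratory system, and the monitor has access to them. The data source list may provide a laboratory dataset, and *Data registration* asks for all relevant data in the CRF.

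Much of this stands. A reader might infer that the passages flatly cannot all be followed. That is too strong: laboratory monitoring can be carried out in full while the eCRF restriction is obeyed, and the conflict with the all-AE rules depends on treating a graded value as an AE. A reader might also infer that laboratory toxicity as a whole is lost. It is not, as the list of what is still recorded shows.

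A third tempting step is to bring in the differing 6-week and 12-week limits, since they affect which delays end treatment. One runs on postponement of treatment, the other on reduction of a related AE; the investigator defines when a delay starts, so the two clocks need not start together. Those passages should be reconciled, but separately.

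The defence does not remove the inconsistency. No laboratory dataset is described; the only routes to the sponsor that the documents describe are the CRF and the serious-event reports. The reading of a graded value as an AE is the protocol's own usage.

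**Conclusion.** The concern holds in a limited form. The eCRF restriction is inconsistent with the role given to laboratory monitoring in the primary endpoint and, on the better-supported reading of what an AE is, with the requirement to record all AEs. It reaches transient, asymptomatic, isolated grade 3 values in seven of the eight listed tests.

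The direction is certain: any omission favours a conclusion of safety. The possible size is one patient deciding the 20% criterion, 2/10 against 1/10. For that to happen there must be a patient whose only grade 3-4 event is such a value, and the analysis must be taken from the eCRF. The documents give no share of laboratory-only grade 3 events, so no probability is offered. They also do not support a claim that the stopping rule would fail; that is possible but less likely.

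**What to change.** Amend the sentence under *Grading of adverse events* so that every laboratory abnormality of CTCAE grade 3 or above is entered in the eCRF with grade and relatedness. Alternatively, export all protocol laboratory values and derive the grades by program.

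State that these events count in the proportion compared with 20% and, where drug related, in the stopping tally, each under its existing wording. Name the data source for each count. No clinical threshold needs to change.

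The cost is a small protocol and CRF amendment. The blood tests are already planned: 1 screening + 16 vaccinations + 2 follow-ups = 19 scheduled safety panels per patient, or 190 for 10 patients, plus any unscheduled repeats. Only values of grade 3 or above need entry. The reported AE rate may look slightly less favourable.

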 - fluid treatment or treatment of nausea
 - blood transfusion
 - platelet transfusion
 - febrile leucopenia/neutropenia
 - administration of investigational procedures
 - placement of a permanent intravenous catheter

These events are to be registered in the eCRF.

Known adverse reactions

Montanide ISA-51:

Montanide ISA-51 has been used in more than 150 clinical trials. Montanide has a well-documented safety-profile. Frequently reported side effects after injection are flu-like symptoms (headache, chills, fever and nausea) while most common local reactions are granuloma, local pain,

inflammation or erythema. These reactions are generally classified as mild to moderate and they are typically transient in nature.

Reference is made in attached drug information leaflet (appendix 11).

Arginase peptide:

The peptide has not been tested in humans, so no adverse reactions have been documented.

Handling adverse events

Autoimmune side effects will be handled according to a local guideline for handling side effects for checkpoint inhibitors based on recommendations by Weber et al⁶³. This guideline is in Danish and named “Vurdering og håndtering af bivirkninger relateret til behandling med ipilimumab, nivolumab og pembrolizumab” and is available online and in print for the physician at duty. In the highly unlikely case that the vaccine induces a cytokine release syndrome, also known as a cytokine storm, the patient will be treated in accordance with the guideline on treatment of cytokine release syndrome recently published by Brudno et al⁶⁴.

Patients will be admitted at the Department of Oncology, Herlev Hospital, in case of occurrence of adverse events related to the investigational treatment that requires hospitalization.

The intensive care unit at Herlev Hospital will be informed of the study, since intensive care support could potentially be required if a treated patient develops anaphylactic shock. The information will be given prior to the start of patient inclusion in the protocol and treatment will not begin before the department management at the intensive care unit has confirmed that the information is received.

Insurance

Patients' participation in the study will be covered by the hospital's liability insurance.

Ethical aspects

This project will potentially add to existing knowledge in the field of immune therapy and help improve treatments and thus prognosis of metastatic solid tumors.

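### Part of the list of events exempt from reporting has no relatedness limit, so for a vaccine-related admission it conflicts with the 24-hour and SUSAR rules

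*Combined protocol and SAP*

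**What the plan says.** Under Serious adverse events, an event is serious if, among other criteria, it "requires hospitalization or prolongation of existing" inpatient stay. Under Adverse reactions, the protocol notes that expectedness is hard to judge in a first-in-human trial and concludes: "Therefore, SARs will be reported as SUSARs".

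Under Reporting of adverse events and adverse reactions, the first rule is "Investigator reports SAEs, SARs and SUSARs to sponsor within 24 hours". The sponsor then reports SARs and SUSARs to the Danish agency "within 7 days if considered life threatening or fatal, and otherwise within 15 days". The sponsor also submits an annual list of SARs and SUSARs, and a final report describing every SAE, SAR and SUSAR.

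The same section then lists what is not to be reported, in three groups:

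- Group 1: "Deaths caused by the malignant disease or progression".
- Group 2: "Hospitalizations or prolongation of current hospitalization caused by the malignant disease", followed by eight items.
- Group 3: "Hospitalizations or prolongation of current hospitalization if the sole reason for hospitalization or prolongation is" one of six items: fluids or nausea treatment, blood transfusion, platelet transfusion, "febrile leucopenia/neutropenia", investigational procedures, or placement of a permanent catheter.

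Events on the list are still entered in the eCRF.

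**The concern.** Groups 1 and 2 cannot contain a reaction to the vaccine, because each is defined by the cancer being the cause. Group 3 is defined only by the reason for admission. It therefore covers related and unrelated admissions alike, and it directly follows rules that require related serious events to be sent promptly.

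For unrelated admissions the list can be read as a deliberate exception to the 24-hour SAE rule, and there is no objection to that. The difficulty is confined to related admissions. Known adverse reactions states that the peptide has never been given to humans, so the protocol offers no basis for presuming that such an admission is unrelated.

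At stake is the timing of safety information. If the list is followed, a related admission reaches the sponsor only through the CRF instead of within 24 hours, and the agency does not receive it within 15 days.

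**Working it through.** There is no figure in the plan to reproduce and no error rate involved. The check compares the text and then applies the rules to a test case.

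**Limits on each group**

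| Group | Items | Limited to the cancer or its progression |
|---|---|---|
| 1 (deaths) | 1 | 1 |
| 2 (admissions caused by the cancer) | 8 | 8 |
| 3 (admissions by sole reason) | 6 | 0 |

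Groups 1 and 2 together: 1 + 8 = 9 of 9 limited. Group 3: 0 of 6.

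Not all six items in group 3 create a conflict. An admission only for an investigational procedure or a catheter would not normally be a SAR. That leaves 6 − 2 = 4 items where a related event is plausible: fluids or nausea, blood transfusion, platelet transfusion, and febrile leucopenia/neutropenia. The last is the clearest case, because it is a medical event and not a procedure.

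**Test case: an admission solely for febrile neutropenia, judged vaccine-related, not life-threatening**

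1. Hospitalisation makes it an SAE.
2. Relatedness makes it a SAR.
3. As a SAR it goes to the sponsor within 24 hours.
4. It is treated as a SUSAR and goes to the agency within 15 days.
5. It is also named in group 3, so it is not to be reported.

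Steps 3 and 4 conflict with step 5, and no sentence says which prevails. A related admission for nausea gives the same result; nausea is among the frequent adjuvant reactions under Known adverse reactions.

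**What remains if step 5 is followed**

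The event is recorded in the chart and the eCRF. Data registration says that CRFs go to the sponsor but sets no deadline. The only timing it gives is CRF entry after the course of treatment, which can last 48 weeks. Monitoring gives the GCP unit access to source documents, with visits described only as regular.

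**Annual list and final report**

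Both are worded to cover all SARs. The exemption does not say whether it applies to expedited reports only or to these documents as well.

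**The case against.** The strongest counter-reading is that general rules followed by a list of exceptions is an ordinary layout, and that the order implies the exception prevails. This explains the text for unrelated events. For related events it settles the conflict only by leaving a SAR without expedited notice, which defeats the stated reason for treating every SAR as a SUSAR.

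A second objection is that febrile neutropenia could be serious on another ground, as a significant medical event, and so stay reportable even if the admission is exempt. The protocol does not say this. The list names the condition itself, so the extra criterion sharpens the clash. A related admission for nausea or fluids does not depend on this argument.

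Third, the practical consequence is narrow, and this stands. The stopping rule counts patients with drug-related grade 3-4 adverse events and does not depend on expedited reports. Safety is reviewed before the second patient, the third patient and the remaining patients are included. Blood counts are among the criteria for delay and exclusion, and related cases needing admission go to the trial's own department. Nor do the documents suggest that such admissions are expected: adjuvant reactions are described as mild to moderate and transient, and the cited IDO vaccine study saw no grade 3-5 toxicity. These points limit the harm, but none of them tells the investigator which instruction to follow.

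**Conclusion.** The concern holds and should be fixed. For a vaccine-related admission that is serious by hospitalisation alone, group 3 contradicts the 24-hour rule and the rule that SARs are handled as SUSARs. Nothing elsewhere in the document resolves it.

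The effect is loss of the 24-hour notice to the sponsor and the 15-day notice to the agency, in exchange for a CRF route with no deadline. Four of the six items can plausibly produce the conflict. Life-threatening or fatal events, which carry the 7-day limit, lie outside this claim because they are serious on other grounds. Data capture and the stopping count are also outside it.

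The conclusion assumes only that the investigator judges an admission of this kind to be related. The documents give no rate for such admissions, so no probability is claimed.

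**What to change.** Reconcile the passages in Reporting of adverse events and adverse reactions:

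- Limit group 3 to events assessed as not related to the vaccine.
- State that any hospitalisation possibly related to the vaccine follows the 24-hour SAE/SAR rule and the SUSAR rule, whatever the reason for admission.
- State that the list does not remove SARs from the annual list or the final report.

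The cost is one or two sentences of wording and perhaps an occasional extra expedited report. No new assessment is needed, because the investigator already judges relatedness under Assessment of safety and Adverse events. No dose, schedule or clinical rule changes.
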